### **Pulmonary function testing protocol**

Bedside spirometry was performed by a trained respiratory therapist using a KoKo Trek USB Spirometer software and pneumotachometer (KoKo, USA). Pulmonary function tests were completed at the time of consultation (prior to the first HBOT treatment) and following every 20 treatments thereafter. In rare cases when PFTs could not be obtained on the exact date of a 20th, 40th, or 60th treatment (e.g., due to equipment limitations), they were obtained on the nearest possible date of another treatment and rounded to an increment of 20 at the time of data analysis. The spirometry equipment was calibrated at the beginning of each day. Patients were tested in a seated position with nose clips, in accordance with American Thoracic Society testing criteria [13], and results were compared against Knudson reference values [14] to determine their percentage of predicted values based on age, sex, and height. To capture potential restrictive, obstructive, and effort-independent changes, three markers of dynamic lung function were recorded: FEV1% (percentage of predicted FEV1), FVC% (percentage of predicted FVC), and FEF25-75% (percentage of predicted FEF25-75). The data utilized in this study comprise the highest readings for each of these variables from three satisfactory forced expiratory maneuvers performed as part of each PFT assessment. The primary outcome of this study was change in spirometry performance over the course of HBOT. We additionally classified the degree of any baseline PFT abnormalities on the basis of each independent parameter's deviation from the

predicted value, designating mild abnormality as 70-79%, moderate abnormality as 60-69%, and severe abnormality as less than 60%.

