### **Data collection and statistical analysis**

Patient demographic data and past medical history characteristics were summarized using descriptive statistics, and continuous data were expressed as means  $\pm$  standard deviations. Linear mixed effect regression models were used to estimate the adjusted sample mean scores of PFT outcomes FEV1%, FVC%, and FEF25-75% at each timepoint for the cohort. Timepoint was included as the fixed effect and individual subject as the random effect for each outcome for the overall cohort. PFT outcomes were also modeled for subgroups by timepoint interaction for pre-existing respiratory disease, smoking status, and treatment pressure (in ATA). Similarly, individual subjects were included as random effects. The maximum likelihood estimation was used to prepare the mixed models and analyzed under the intention-to-treat principal. Post-hoc pairwise comparisons between timepoints were conducted for each grouping of pre-existing respiratory disease, smoking status, and treatment pressure, for each PFT variable. Pairwise comparisons were adjusted using Tukey's HSD. The alpha was set to 0.05. All analyses were performed using R version 4.0.3.

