### **Objectives**

The primary objective of this study was to evaluate changes in series of pulmonary function tests (PFTs) performed over the course of recurrent HBOT exposures. A secondary study outcome was the incidence of pulmonary complications such as lung barotrauma.

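### Does testing three spirometry variables, each at alpha 0.05, call for a multiplicity correction across them?

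*Combined protocol and SAP*

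**What the plan says.** The section *Pulmonary function testing protocol* states the primary outcome in general terms: "The primary outcome of this study was change in spirometry performance over the course of HBOT". In the same section "three markers of dynamic lung function were recorded", namely FEV1%, FVC% and FEF25-75%, chosen to pick up restrictive, obstructive and effort-independent change respectively. The *Objectives* section is just as general; the aim is to "evaluate changes in series of pulmonary function tests (PFTs) performed over the course of recurrent HBOT exposures".

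The section *Data collection and statistical analysis* fits one model per variable: "Timepoint was included as the fixed effect and individual subject as the random effect for each outcome for the overall cohort". The stated use of these models is to estimate mean values at each timepoint. Subgroup models follow, and then "Post-hoc pairwise comparisons between timepoints were conducted for each grouping of pre-existing respiratory disease, smoking status, and treatment pressure, for each PFT variable". Error control is covered by "Pairwise comparisons were adjusted using Tukey's HSD. The alpha was set to 0.05". No main variable, testing order, joint test or division of alpha is given. No test of the timepoint effect in the whole cohort is named.

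**The concern.** One primary outcome is measured three ways, and each way has its own test at 0.05. A reader used to confirmatory trials will ask what has to happen for spirometry to count as changed. If one significant variable out of three is enough, the real error rate for the primary outcome is above the stated 5%. The plan does adjust for multiplicity within each variable, which makes the silence across variables look like an oversight.

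The subgroup comparisons add to this. They repeat the timepoint comparisons for every grouping and every variable at the same alpha, so an isolated significant result is likely somewhere. At stake is whether a chance finding in one variable or one subgroup could be reported as an effect of hyperbaric oxygen on the lungs.

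**Working it through.** **Inputs from the documents.** Alpha 0.05; three variables in separate models; Tukey within a model; tests before treatment and after every 20 sessions, with the 20th, 40th and 60th named, so up to four timepoints. The plan gives no familywise error, sample size or power figure, so there is none to reproduce.

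**Assumptions.** Two-sided tests; a common correlation r between the variables' test statistics; large-sample normality. The documents do not give r, so a range is shown.

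**Step 1: any one variable counts, r = 0.** 1 − 0.95³ = 1 − 0.857 = 0.143, or 14.3%.

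**Step 2: any one variable counts, r > 0.** Simulation under no change, four timepoints, 300,000 draws (1,000,000 for the last column):

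| r | Tukey range test per variable | Overall timepoint test per variable | Single test per variable at 0.05/3 |
|---|---|---|---|
| 0 | 14.3% | 14.3% | 4.9% |
| 0.5 | 12.8% | 12.7% | 4.4% |
| 0.8 | 10.3% | 10.1% | 3.5% |
| 0.9 | 8.7% | 8.6% | 3.0% |
| 0.95 | 7.6% | 7.5% | 2.6% |

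Three timepoints instead of four give results within about 0.3 percentage points. Each variable alone stays at 5.0%, so Tukey does its job within a variable. All three readings come from the same set of breathing manoeuvres, so r = 0 is an upper limit and not a likely value.

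**Step 3: other reading rules.** If each marker answers its own question, the error rate per question is 5%. If all three had to change, the joint error could not exceed 5%; at r = 0 it would be 0.05³ = 0.000125. Inflation therefore arises only under the any-one rule, and the plan does not state that rule.

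**Step 4: subgroups.** Assuming two levels per factor, 3 factors × 2 levels × 3 variables = 18 Tukey families, and 18 × 0.05 = 0.9 false-positive families are expected. With full independence the chance of at least one would be 1 − 0.95¹⁸ = 60%. Simulation with an assumed 200 patients and assumed factor frequencies of 30%, 40% and 60% gives 53% at r = 0 and about 32% at r = 0.95. None of these inputs except the number of factors and variables is in the documents.

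**Step 5: price of a correction.** Take 80% power per variable as an assumption (3 df, noncentrality 10.90). At 0.05/3 power falls to 66.1%. Under Holm, with equal change in all three variables, average power is 75.1% at r = 0 and 70.9% at r = 0.95. If the Tukey pairs were also tested at 0.05/3, the critical value would rise from 2.569 to 2.952, a ratio of 1.149, so intervals would be about 15% wider.

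**The case for a change.** The best case for a change is that the plan has already opted into error control. It declares a primary outcome, sets an alpha and adjusts pairwise comparisons, so calling the study exploratory does not fully answer the point. The outcome is worded as one thing, and nowhere does the plan say that the three markers are to be read separately. A rule would need only a few sentences, and showing unadjusted estimates beside adjusted results would limit the risk of hiding a real decline.

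Part of this stands. The scope of alpha is unstated, the whole-cohort comparison is unnamed, and the arithmetic is right under the any-one rule. A single significant variable should not be presented as a 5%-level finding for spirometry as a whole.

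The rest is weaker. The 7.5% to 14.3% describes whole-cohort tests that the plan does not name, combined by a rule it does not contain. The subgroup comparisons are already labelled post hoc, so calling them exploratory would add little. Holm is also not a matter of wording alone: the methods are written in the past tense, and if the analysis has been done, a correction chosen now would itself be post hoc. Missing a true decline matters in a study that also counts pulmonary complications as a secondary outcome.

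**Conclusion.** No change is needed. The observation is accurate, but it does not show an error. The any-one false-positive chance is 14.3% at r = 0 and about 7.5% at r = 0.95, and it applies only if one significant variable is taken as a positive primary result. Nothing in the plan says that it would be, and the distinct purposes given to the three markers support reading each at its own 5%.

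Correction across the variables is a trade-off on which competent statisticians differ: tighter control of a claim the plan does not make, against a loss of roughly 5 to 14 percentage points from an assumed 80% power (80 − 75 to 80 − 66). For an estimation-focused retrospective cohort, leaving the variables uncorrected is a fair choice. What remains is detail that a competent analyst supplies when reporting: alpha understood as per variable, each marker shown with its estimate and 95% interval, and isolated subgroup results treated as exploratory.

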### **Objectives**

The primary objective of this study was to evaluate changes in series of pulmonary function tests (PFTs) performed over the course of recurrent HBOT exposures. A secondary study outcome was the incidence of pulmonary complications such as lung barotrauma.
